6.0 STUDY PROCEDURES

6.1 Informed Consent

Before study initiation, the clinical protocol, the Informed Consent Form (ICF), and any advertisements for subject recruitment will be submitted for review and approval to the Institutional Review Board (IRB). The investigator, or his designated research staff, will obtain written informed consent from each subject enrolled in the study, in accordance with the U.S. Food and Drug Administration (FDA) regulations 21 CFR parts 50.20-50.27. It is the responsibility of the investigator to ensure that informed consent is obtained from the subject or his/her guardian or legal representative before any activity or treatment is undertaken which is not part of routine care.

6.2 Subject Identification Code

All subjects who sign an ICF will be assigned a subject code. The code assigned will not contain any identifying information. The subject code will be used to identify the subject for the rest of the study.

6.3 Safety Assessments

Safety will be evaluated by the incidence, severity, and relationship to treatment agent of adverse events.

6.3.1 Monitoring for Adverse Events: Details of all AEs that occur after the first dose of study drug will be collected as indicated in Section 12. Any illness or injury that occurs

before the first dose of a study drug will be recorded under Medical History and evaluated to determine if the occurrence affects the patient's eligibility to participate in the study. Subjects will be asked the following standard questions by the designated clinical evaluator:

At clinic check-ins:

1. "Have you had any medical problems since your last visit?"
2. "Have any medical problems present at your last visit changed, i.e., stopped, worsened, or improved?"
3. "Have you taken any medicines, other than study drug, since your last visit?"

Any spontaneous AE information provided by the patient will be recorded.

NOTE: An AE may be a new disease(s), any untoward event(s), or an exacerbation of a pre-existing condition. See Section 12.0 for complete details.

6.4 Adipose biopsy:

Approximately 500-1000 mg of subcutaneous adipose tissue will be biopsied from the gluteal region, processed, weighed and frozen until analyzed. Adipose tissue will be obtained through a small (~5mm) incision under local anesthesia (2% Lidocaine without epinephrine), as has been previously described¹³⁻¹⁵. A portion (200 mg) of the samples will be flash frozen and analyzed for gene expression and protein assays. Another portion (500-800 mg) will be placed in sterile media and undergo digestion with collagenase, filtration, and centrifugation for separation of the stromal vascular fraction (SVF). SVF cells will be stained with antibodies for flow cytometer analysis. Finally, remaining tissue will be fixed in paraffin for immunohistochemistry.

6.5 Subgingival analysis

Saliva samples will be collected using the OMNIgene DISCOVER (OM-505) kit (DNA Genotek), an all-in-one kit which collects and stabilizes both microbial DNA and RNA in saliva. Samples will be stored at -80C prior to extraction. Nucleic acids will be extracted using the QIAGEN QIAamp MinElute Virus Spin Kit (Qiagen). Subgingival plaque samples will be obtained from 3 oral cavity regions in each subject (2 samples per region) using a soft-bristled microbrush (DenTek). Specimens will be collected from the same anatomical location in all subjects. DNA will be isolated using the PSP Spin Stool DNA kit (Invitex). DNA samples will be amplified using V1-V2 region primers targeting bacterial 16S genes and sequenced using IlluminaHiSeq or 454 Pyrosequencing technology.

6.6 Specific Study Procedures (by visit)

A detailed study time-table and list of all procedures to be performed at each visit is included in Appendix A.

6.6.1 Screening (Visit 1)

Potential participants will be screened first by a telephone or e-mail interview with the

research coordinator (see Appendix B for email interview form; for telephone interviews this information will be verbally exchanged). Participants who meet initial study requirements will be invited for a screening visit (visit 1) at the CTRC. Prior to this visit, participants will receive a detailed health questionnaire (see Appendix C) that has been used in numerous previous studies that addresses questions regarding past medical history, current use of medications and dietary supplements, exercise and social habits. In addition, participants will be asked about fish consumption in order to ensure recruitment of subjects with lower EPA + DHA intake during the study period. Participants will be asked to complete these questionnaires at home and bring the completed forms with them to their screening visit. During the screening visit, they will meet with research staff to review and sign an IRB-approved consent form. Research staff will review the health questionnaire with the participant as well as measure weight, height, waist and hip circumference, sitting blood pressure and heart rate. A brief physical exam will be performed as well as an electrocardiogram (ECG). In addition, participants will have blood drawn (after a 12 hour fast) for evaluating fasting lipids, glucose, serum chemistries and liver function and a complete blood count. Female participants will also be asked to provide a urine sample for a pregnancy test. These laboratory parameters are included to assure the participant meets eligibility criteria and that he/she is generally in good health. Once all clinical data has been reviewed, study personnel will contact each study volunteer to let them know if they are eligible.

6.5.2 Randomization visit (Visit 2)

One to four weeks after the screening Visit 1, eligible participants will return to the CTRC after a 12 hour fast for a 2 hour visit. Participants will be asked to brush their teeth after their last meal the day before the visit, or at the start of the 12-hour fasting period, and to refrain from additional brushing or use of mouthwash until after the study visit. Participants will meet with a research nurse / coordinator who will assess any change in medical history and medication use, as well as review any adverse events. Blood pressure, heart rate, height and weight will be measured, blood and urine will be collected for pre-randomization baseline efficacy measures and a urine pregnancy test performed for all females. The simple fish consumption questionnaire will be administered to assess any changes to the level of omega-3 intake in the diet.

They will also be asked to record all food and beverages consumed on dietary records on 3 days prior to the visit, as well as completing a digestive health questionnaire and diet history questionnaire. All nutrient data collected from 3-day dietary records will be analyzed by Food Processor 8.1 (06/03, Escha). Participants will be asked to complete these questionnaires at home and bring the completed forms with them to their study visit. If a subject is unable to print out or complete the forms at home, they will be completed at the visit.

Saliva and subgingival plaque samples will be taken for assessment of oral microbiome. Saliva samples will be collected using a standardized kit. Under the supervision of study personnel, subjects will be given the kit, which consists of a funnel attached to a tube, and instructed to spit into the funnel until the amount of liquid reaches a fill line located on the outside of the attached tube. Once the proper amount has been collected, the lid of the funnel will be closed and the funnel removed from the tube. The tube is then

capped and shaken for about 10 seconds. Subgingival plaque samples will be collected by swabbing several regions of the buccal mucosa using microbrushes. A separate brush will be used for each swab and two samples will be collected from each region.

In order to establish effects of treatments on adipose inflammatory parameters, we will obtain gluteal region subcutaneous adipose tissue biopsies under local anesthesia (2% Lidocaine). A detailed description of the adipose collection procedures is given in Section 6.4. Participants will then be randomized to drug or placebo group. Supplies of study drug will be provided to last 8 weeks (4 pills/day of either Lovaza or placebo).

Participants will be provided verbal and written instruction to take the study drugs as follows; 2 fish oil/placebo with food in the morning, 2 fish oil/placebo with food in the evening. A pill diary will be given to all subjects.

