GPR120 is a LC n-3 PUFA receptor and may inhibit NFκB signaling: Recent work suggests the effects of LC n-3 PUFA on obesity-related inflammation are mediated via interactions GPR120, a G-protein-coupled receptor (GPR), which is highly expressed on adipocytes and macrophages⁴⁹. GPR120 is part of the G α q-linked GPR family and stimulation results in increased intracellular Ca⁺⁺ and ERK activation⁵⁰. Compared to wild-type mice GPR120 deficient mice fed a HFD have increased weight, insulin resistance, circulating and adipose inflammatory markers—including the chemokine CCL2, and ATMs⁵¹. Remarkably, humans with a dominant-negative loss-of-function variant in *GPR120* (R270H) have increased incidence of obesity⁵¹. In 3T3-L1 adipocytes, siRNA knockdown of GPR120 reduced expression of insulin signaling genes⁵². Highlighting its role as an LC n-3 PUFA receptor, GPR120 deficiency blocks the benefits of LC n-3 PUFA supplementation to HFD in mice, agonists to GPR120 mimic effects of DHA to block LPS-induced NFκB activation in macrophages, and knockdown of GPR120 abolishes DHA effects⁴⁹. Whether GPR120 deficiency modulates EPA effects is not reported, notably anti-inflammatory effects of EPA occur via distinct changes in plasma cell membranes in immune cells⁵³.

LC n-3 PUFA may affect the oral microbiome

Periodontal disease has been associated with increased risk of cardiometabolic diseases^{54,55}. There is data that suggests that dietary fat intake, including omega-3 fatty acids affect the composition of the intestinal and oral microbiome^{56,57}. The direct effect of LC n-3 PUFA supplementation on oral microbiome composition and the relationship between inflammatory chemokine pathways and the microbiome have not previously been evaluated.

Overall LC n-3 PUFA modulate chemokine signaling including adipocyte and macrophage inflammation, ATM infiltration, and monocyte activation; these actions may be mediated, at least partially, via GPR120 and NFκB. However, no human studies examining the effect of LC n-3 PUFA on the CCL2 and CX3CL1 adipochemokine pathways have been reported and the role of GPR120 and NFκB on these pathways has not been explored. Insight into LC n-3 PUFA action on these functional pathways may clarify mechanisms and guide therapeutic developments in human.

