6.5.4 Completion Visit (Visit 4)

Participants will come to the CTCRC after a 12 hour fast. Participants will meet with a study coordinator who will assess changes to the medical history and medication use. They will also be asked to record all food and beverages consumed on dietary records on 3 days prior to the visit. Any adverse events will be recorded, pill diary reviewed, and study medications will be counted (pill count) Weight and height will be recorded and BMI calculated. ECG will be performed. Blood will be drawn for post-drug screening of liver functions and chemistries as well as for all outcome-related measures (lipids, insulin/glucose, inflammatory markers). Urine for efficacy measures will also be collected. Urine pregnancy test will be performed in all females. Saliva and subgingival plaque samples will be taken to assess for any change in oral microbiome by the treatment. An adipose biopsy will be performed as per Section 6.4.

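### The Visit 2 instruction takes the subgingival plaque swab from the cheek lining, so this specimen of the exploratory microbiome aim has contradictory site instructions

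*Combined protocol and SAP*

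**What the plan says.** Section 6.5 (Subgingival analysis) describes two oral specimens: saliva collected with a kit, and plaque. For the second it says: "Subgingival plaque samples will be obtained from 3 oral cavity regions in each subject (2 samples per region) using a soft-bristled microbrush". It adds: "Specimens will be collected from the same anatomical location in all subjects". It does not name the regions or the location, and it does not mention the cheek.

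Section 6.5.2 (Visit 2, printed after Section 6.6.1) first names the same two specimens: "Saliva and subgingival plaque samples will be taken for assessment of oral microbiome". A few sentences later it tells staff how to take the second one: "Subgingival plaque samples will be collected by swabbing several regions of the buccal mucosa using microbrushes". It also asks for two samples per region.

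Section 6.5.4 (Visit 4) says: "Saliva and subgingival plaque samples will be taken to assess for any change in oral microbiome by the treatment". It gives no surface, regions or number of swabs. Appendix A schedules saliva at Visits 2 and 4 and has no line for the swab.

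The microbiome aims are exploratory hypotheses 3 and 4 and objective 10 in Section 3.0. They refer to the oral microbiome in general and name no site.

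**The concern.** The specimen's name and the instruction for taking it point to different places in the mouth. Section 6.5.2 is the only text that tells staff which surface to swab, so it is the text a coordinator would act on.

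Two things could go wrong:

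- **The instruction is followed consistently.** Cheek swabs are then sequenced and reported as subgingival plaque.
- **Different sites are used at different visits or by different staff.** Visit 4 is silent, so a coordinator could swab the cheek at baseline as Section 6.5.2 says and the gum margin at Week 8 as the specimen's name implies. A change in bacterial composition within a participant would then mix a site difference with a change over time. Hypothesis 3 concerns treatment-related change, and hypothesis 4 correlates that change with diet and metabolic measures.

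Neither fault could be repaired after sequencing unless the site of each swab had been recorded, and the protocol does not ask for that.

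**Working it through.** The plan states no figure on this point to reproduce. The check is a comparison of the text, followed by a count of the swabs involved.

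**Comparison of the text**

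| Place | Specimen named | Surface to swab | Regions |
|---|---|---|---|
| Section 6.5 | Subgingival plaque | Not named; to be the same in all subjects | 3, two samples each |
| Section 6.5.2 (Visit 2) | Saliva and subgingival plaque | Buccal mucosa | Several, two samples each |
| Section 6.5.4 (Visit 4) | Saliva and subgingival plaque | Not stated | Not stated |
| Appendix A | Saliva only | Not applicable | Not applicable |
| Section 3.0 | Oral microbiome | Not stated | Not stated |

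1. By the meaning of the words, subgingival plaque is on the tooth surface below the gum margin, and buccal mucosa is the lining of the cheek. A swab of the second does not collect the first. The Section 6.5.2 sentence therefore contradicts itself, and it contradicts the specimen named in Sections 6.5 and 6.5.4.
2. No row of the table resolves this. The Section 6.5 rule on a common location does not say what the location is, and it is worded across subjects, not across visits within a subject.
3. The number of regions also differs: three in Section 6.5, an unspecified several in Section 6.5.2.

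**Swabs exposed to the ambiguity**

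Inputs: 3 regions and 2 samples per region (Section 6.5); swabs at Visits 2 and 4 (Sections 6.5.2 and 6.5.4); about 52 randomised and 44 completing (Section 5.1).

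- Per participant per visit: 3 x 2 = 6.
- Visit 2, all randomised: 52 x 6 = 312.
- Visit 4, completers only: 44 x 6 = 264.
- Total: 312 + 264 = 576.

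The total assumes that participants who drop out give no Visit 4 swab. Counting completers only gives 44 x 12 = 528. If all 52 attended both visits, it would be 52 x 12 = 624.

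**The case against.** The strongest reply is that this is a drafting slip with little consequence. Much of that is right:

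- Saliva is a separate microbiome specimen, collected at both visits, and the swab wording does not touch it.
- Hypotheses 3 and 4 are worded for the oral microbiome as a whole, so both could still be examined in saliva. A cheek swab taken consistently would also be an oral specimen, usable for change over time under its correct name.
- Section 6.5 already asks for a common location across subjects, and nothing shows that staff would split between sites.
- The trial is randomised and double blind, so a site error would have no evident reason to favour one arm. The damage would fall mainly on within-person change and its correlations, and as noise in the comparison between arms.

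A reader might infer that the microbiome hypotheses become uninterpretable because the aim is a periodontal one. The documents do not support that. Section 2.0 does open the topic with "Periodontal disease has been associated with increased risk of cardiometabolic diseases", but it goes on to dietary fat and the intestinal and oral microbiome, and states the gap as the effect of supplementation on oral microbiome composition. No endpoint is a periodontal or plaque-specific measure. Nor can a reader infer that several hundred specimens are wrong: the count shows how many depend on the wording, not how many were mis-sampled.

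The contradiction itself is not answered. Calling it a slip does not change what a coordinator would do when following the sentence, and the common-location rule would be satisfied by sampling everyone's cheek.

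**Conclusion.** This is an internal inconsistency, and Section 6.5.2 is wrong as written. It is limited to the swab specimen of an exploratory aim. If the instruction is followed, the swab results could not be reported as subgingival plaque. If sites differ between visits, within-person change in the swab data is confounded with site.

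About 576 swabs are exposed, on the assumptions of 52 at Visit 2, 44 at Visit 4 and six swabs per visit. How many would come from the wrong site cannot be known from the documents.

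Saliva, the primary endpoint (plasma CX3CL1), the secondary endpoints and the sample size are unaffected. The point is minor, and worth making because the correction costs almost nothing before sampling and cannot be made after sequencing without a record of site.

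**What to change.** Reconcile Sections 6.5, 6.5.2 and 6.5.4 so that one named site and the same three named regions apply at Visits 2 and 4. There are two ways to do this:

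- correct the Section 6.5.2 instruction to the gingival margin or sulcus, keeping the name subgingival plaque; or
- keep the cheek as the site, rename the specimen as buccal mucosal throughout, and report it as such.

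In either case, record the site of each swab on the case report form, and add the swab to the Appendix A schedule beside saliva. The cost is a corrected sentence (or the renaming), a field on the form, a line in the schedule and a staff briefing. No extra swabs, visits or participants are needed.

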6.5.3 Telephone / E-mail Follow up (Visit 3)

Participants will be contacted by telephone or e-mail approximately four weeks (visit 3) post-randomization to review medication compliance and pill diary, adverse events and any changes in fish consumption. Participants with <80% apparent adherence to study medication will be counseled to increase compliance so that their adherence at 8 weeks will be $\geq 80\%$.

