10.3 Study Agent Compliance

Study drug adherence will be monitored by pill count and medication diary and will be assessed by telephone/email contact at 4 weeks after randomization and in person at Visit 4 (8 weeks after randomization). The final analysis of compliance will be performed at this time.

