APPENDIX A

Study Visits and Procedures

Procedure	Visit 1	Visit 2	Visit 3	Visit 4
	Screen	Randomization	Contact Follow-up	Completion
	Week -2 to -4	Week 0	Week 4	Week 7-9
Participant Questionnaire completion ¹	X			
Informed consent	X			
History & physical	X			
3 day diet record, Food History questionnaire		X	X	
Electrocardiogram	X			X
Blood pressure, heart rate, weight, height & waist measures	X	X		X
Glucose and insulin measurement	X			X
Urine pregnancy test ²	X	X		X
Review medications	X	X	X	X
Dispense study medication/placebo pills		X		
Comprehensive Metabolic Lab Panel ³	X			X
Complete blood count (CBC)	X			X
Lipid profile ⁴	X			X
Blood and urine collected for efficacy measures		X		X
Dietary assessment of high omega-3 fish consumption (questionnaire)	X	X	X	X
Saliva Collection		X		X
Adipose biopsy		X		X

- ¹ The questionnaire along with a copy of the consent form will be mailed to subjects for completion prior to the study visit in order to save time on the day of their screening visit. After consent is obtained, a coordinator will review the questionnaire with the participant for completeness.
- ² Standard urine pregnancy test performed on females of child-bearing potential only
- ³ Comprehensive Metabolic panel includes: sodium, potassium, chloride, carbon dioxide, glucose, blood urea nitrogen, creatinine, calcium, total protein, albumin, AST, ALT, alkaline phosphatase, and total bilirubin
- ⁴ Includes TC, LDL-C, VLDL, HDL-C, TG

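### Capsules are dispensed once for 8 weeks, but the completion visit may fall as late as week 9, so the best adherers can give the only post-treatment CX3CL1 sample and second biopsy off drug

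*Combined protocol and SAP*

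**What the plan says.** - **Supply.** Section 6.5.2 (Visit 2): "Supplies of study drug will be provided to last 8 weeks (4 pills/day of either Lovaza or placebo". No overage is mentioned.
- **Dispensing.** The Appendix A row "Dispense study medication/placebo pills" is marked at Visit 2 only.
- **Visit 3.** Section 6.5.3: "Participants will be contacted by telephone or e-mail approximately four weeks (visit 3) post-randomization". No resupply is described.
- **Visit 4 timing.** Appendix A allows weeks 7 to 9. Section 10.3 gives the nominal time: "in person at Visit 4 (8 weeks after randomization".
- **Visit 4 sampling.** Section 6.5.4 has blood drawn "as well as for all outcome-related measures (lipids, insulin/glucose, inflammatory markers", and adds: "An adipose biopsy will be performed as per Section 6.4". In Appendix A, efficacy blood is collected at Visits 2 and 4 only.
- **Adherence records.** Section 6.5.2: "A pill diary will be given to all subjects". Section 6.5.4 has the "pill diary reviewed, and study medications will be counted (pill count" at Visit 4.

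The documents do not tell participants to keep dosing until Visit 4, and they set no maximum interval between last dose and sampling.

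**The concern.** The supply ends at day 56 and the visit window ends a week later. Visit 4 provides the only post-treatment measurement of plasma CX3CL1, the primary endpoint, and of the adipose endpoints, so no on-treatment sample exists to fall back on.

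The gap falls on the participants who take their capsules most reliably. Someone who misses doses still has capsules in week 9; someone who misses none does not. If the drug's effect wanes after stopping, off-drug samples in the Lovaza arm would tend to pull the treatment contrast towards zero. The placebo arm would not change. The risk is lost sensitivity, not a false positive.

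**Working it through.** **Inputs**
- 4 capsules a day, supply for 8 weeks (Section 6.5.2).
- One dispensing, at Visit 2; Visit 4 in weeks 7 to 9 (Appendix A). With randomization as week 0, this is read as days 49 to 63.
- Adherence threshold of 80% (Sections 6.5.3 and 6.6).
- Assumptions: no overage, constant adherence, participants dose until the capsules run out, and first dose on day 0. The first-dose day is not stated, so day 1 is also shown.

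**1. Supply.** 4 × 56 = 224 capsules. Cover to day 63 needs 4 × 63 = 252, a shortfall of 28.

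**2. How long the supply lasts.** Days covered = 224 / (4 × adherence). Gap at day 63 = max(0, 63 − days covered). Starting on day 1 moves the run-out one day later.

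| Adherence | Days covered | Gap at day 63, start day 0 | Gap at day 63, start day 1 |
|---|---|---|---|
| 100% | 56.0 | 7.0 | 6.0 |
| 95% | 58.95 | 4.05 | 3.05 |
| 90% | 62.2 | 0.8 | 0 |
| 88.9% (56/63) | 63.0 | 0 | 0 |
| 80% | 70.0 | 0 | 0 |

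**3. Average over all visits.** The documents give no distribution of visit days, so two are assumed, both with a day-0 start:
- Even spread over the 15 days from 49 to 63: 28/15 = 1.87 days at 100% adherence, 10.26/15 = 0.68 at 95%, 0.78/15 = 0.05 at 90%.
- Triangular around day 56, with weights 8 − |d − 56| summing to 64: 84/64 = 1.31 days at 100%, 20.8/64 = 0.33 at 95%, 0.78/64 = 0.01 at 90%.
- All visits by day 56: zero.

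**4. Would existing rules flag it?** A participant who takes all 224 capsules and attends on day 63 has taken 224/252 = 88.9% even when every day up to the visit is counted. That is above the 80% threshold, so the adherence rule does not pick up the gap.

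**5. What dilution could do to power (illustration only).** Section 9.1 states 22 per arm for 80% power at 0.9 SD with a Wilcoxon test. That reproduces: simulated power with normal data is 0.81. A t-test approximation gives 0.83 and is the reference below. If a share f of the Lovaza arm is sampled off drug and keeps a share r of the effect, the mean difference becomes 0.9 × [1 − f(1 − r)] SD:
- f = 10%, r = 50%: 0.855 SD, power 0.79.
- f = 25%, r = 75%: 0.844 SD, power 0.78.
- f = 25%, r = 50%: 0.787 SD, power 0.72.

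Neither f nor r can be taken from the documents. These figures show how sensitive power would be; they do not estimate the loss.

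**The case against.** The case for leaving this alone has several parts.

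- **No harm is shown.** Nothing in the documents says how quickly EPA/DHA or CX3CL1 would move after stopping, so a gap of a few days may change nothing. This stands, and it limits the importance of the point.
- **The worst case is rare.** Seven days needs perfect adherence, a visit on the last permitted day and no spare capsules. Under the triangular assumption at 95% adherence, 15/64 (23%) would run out, with a mean gap among them of 20.8/15 = 1.4 days. At 100% adherence it is 28/64 (44%) and 84/28 = 3 days. Losing half the effect in that time has no support in the documents. This also stands, and it counts against the 0.72 power figure in particular.
- **Seven days is slightly too long.** If the first dose is on the evening of Visit 2 and the last is due the evening before a day-63 visit, 2 + 62 × 4 = 250 capsules are needed. The shortfall is 26 capsules, or 6.5 days. That is fair, and it lies within the 6.0 to 7.0 days shown. Every participant also arrives after a 12-hour fast, so some interval from the last with-food dose is normal.
- **The supply matches the stated 8-week regimen.** A late attender who finishes the supply has had the planned exposure. But the same window allows a week-7 visit with shorter exposure, so the plan does not hold exposure fixed. On this reading a week-9 sample is a post-treatment sample, which the plan does not acknowledge.
- **The diary and pill count will show who ran out.** Largely true, but knowing it afterwards does not recover an on-drug sample, and Section 9.2 says nothing about time since last dose.
- **Overage may exist in pharmacy materials.** Possible. A sentence in the protocol would settle the supply question, though participants would still need to be told to keep dosing until the visit.

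**Conclusion.** The concern holds. As written, the plan allows a highly adherent participant to be sampled off drug at the only post-treatment timepoint without any deviation. The gap is at most 6 to 7 days, depending on when the first dose is taken. It requires a visit after day 56 and, at day 63, adherence above 88.9% with a day-0 start. Under the assumed visit-day distributions the average gap is 1.3 to 1.9 days at full adherence, 0.3 to 0.7 at 95%, and 0.01 to 0.05 at 90%. All of this assumes no overage beyond the stated 8 weeks.

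The effect on the CX3CL1 and adipose contrasts cannot be derived and may be small. The importance is modest; the reason to act is that the correction is cheap.

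**What to change.** Dispense a 9-week supply at Visit 2 (4 × 63 = 252 capsules). Instruct participants to keep dosing through the evening before Visit 4. At Visit 4, take the last-dose date from the pill diary.

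The cost is 28 more capsules per participant, or 28 × 52 = 1,456 for the roughly 52 randomized. The last-dose date uses a diary already reviewed at that visit. The drawback is that late attenders would receive up to 9 weeks of treatment, slightly beyond the stated 8-week regimen. If that is unwelcome, closing the window at day 56 also removes the gap, at the price of tighter scheduling.
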